3.4. Study Duration

The treatment duration for individual patients will vary depending on the number of doses of a long-acting *E. coli*-derived asparaginase remaining on a patient's original treatment protocol (completion of each patient's planned asparaginase treatment). Each patient will be followed for at least 30 days following their last dose of the last course of RC-P. If an individual patient has one course of RC-P their study duration will be approximately 72 days (including a Screening period of up to 28 days, one course of treatment [6 doses of treatment over a 2 week period], and a follow-up assessment for safety occurring 30 days after the patient's last dose in their last course of RC-P). Additional courses of RC-P will be administered based on each patient's original treatment plan for as long as the patient derives clinical benefit; subsequent scheduled doses of a long-acting *E. coli*-derived asparaginase remaining on the patient's treatment plan will be replaced by 6 doses (6 doses are equivalent to a course) until their asparaginase treatment has been completed.

The overall study (Part A and Part B) will be deemed complete once all enrolled patients have completed all of their planned courses of RC-P, including 30 days of safety follow-up and additional time as needed for follow-up assessments, or discontinued the study early. The final analysis will be conducted at this time (see [Section 8](#) for descriptions of the possible analyses [interim, primary, and final]).

The overall total study duration to complete enrollment and all patient courses, including 30 days of safety follow-up and additional time as needed for follow-up assessments, for Part A (IM) and Part B (IV) at the investigative sites will be approximately 2 years.

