6.7.6.5. Adverse Event Recording and Reporting

The Investigator must record all AEs that occur from the time written informed consent is obtained until 30 days after the patient's last dose of the last course of RC-P, regardless of their relationship to study drug.

In addition, any SAE assessed as related to study drug by the Investigator that occurs more than 30 days after the patient's last dose of the last course of RC-P, must be reported as described below.

Serious AEs must be reported to the Sponsor or its designee using an SAE Reporting Form within 24 hours of first knowledge of the event by study site personnel. The reporting form and contact information for submission of the form, will be provided to the study sites separately.

The reporting form must be completed as thoroughly as possible before transmittal to the contact provided on the form. The Investigator must provide his/her assessment of causality to the study drug and study procedure at the time of an initial SAE report. If the Investigator's assessment of causality changes after the initial report, it must be provided as follow-up information to the Sponsor.

Other Reportable Experiences:

Overdose, (defined as any dose administered or received that was higher than the intended dose), medication errors (defined as any unintentional error in the dispensing or administration of the study drug), and misuse of the study drug are considered reportable experiences and should be reported by study site personnel on an Other Reportable Experience Form. The form, and contact information for submission of the form, will be provided to the study sites separately.

If any overdose, medication error or misuse of the study drug results in an AE this must be recorded, and if this AE is serious it must also be reported as described above.

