6.7.6.6. Follow-up of Adverse Events

All AEs and SAEs assessed as not related to study drug, including clinically significant laboratory tests, or physical examination findings, must be followed until the event resolves, the condition stabilizes, the event is otherwise explained, or the final study visit occurs, whichever comes first.

Adverse events and SAEs assessed as related to study drug, and AEs and SAEs resulting in discontinuation of study drug or study termination should be followed for as long as necessary to adequately evaluate the patient's safety, or until the event stabilizes, or the patient is lost to follow up. If the event resolves during the study, a resolution date should be recorded, for both AEs and SAEs. If at the time of the final scheduled study visit, the AE is not resolved, the

outcome at that time should be recorded. Once the final outcome is determined for an SAE this information should be provided as follow-up SAE information.

The Investigator is responsible for ensuring that follow-up includes any supplemental investigations indicated to elucidate the nature and/or causality of the event. This may include additional clinical laboratory testing or investigations, examinations, histopathological examinations, or consultation with other health care professionals as is practical, according to Jazz Pharmaceuticals' requests.

The Investigator should provide follow-up SAE information for any updates to information previously provided to Jazz Pharmaceuticals.

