APPENDIX 1. SCHEDULE FOR PROCEDURES AND ASSESSMENTS**Monday Start**

Assessment ^a	Screening	Course 1 and Subsequent Courses														EOS ^h	
		1	2	3	4	5	6	7	8	9	10	11	12	13	14		
Study Day	-28 to -1	M	T	W	Th	F	Sa	Su	M	T	W	Th	F	Sa	Su	14	30 days (±3) after last dose
Weekday		M	T	W	Th	F	Sa	Su	M	T	W	Th	F	Sa	Su		M-F
Informed consent	X																
Prior Medications	X																
Demographics	X																
Medical History	X																
Height	X	X ^b															
Weight	X	X ^b															
Physical Examination ^c	X	X ^d															X
Vital Signs and Temperature ^c	X	X								X							X
Local Lab Urine Pregnancy Test (Females of Child-bearing potential)	X ^e	X ^e															X
Local Lab Serum Chemistry ^f	X ^g	X ^g															X
Local Lab Hematology (CBC) ^f		X															X

RC-P

Jazz Pharmaceuticals Ireland Limited

Protocol Amendment 02: JZP458-201

Assessment ^a	Screening	Course 1 and Subsequent Courses														EOS ^h		
		1	2	3	4	5	6	7	8	9	10	11	12	13	14			
Study Day	-28 to -1																	30 days (± 3) after last dose
Weekday		M	T	W	Th	F	Sa	Su	M	T	W	Th	F	Sa	Su			M-F
Local Lab Coagulation ^f		X																
RC-P Drug Administration (IM or IV)		X		X		X			X				X					
Pharmacokinetics		Refer to Appendix 2																
Pharmacodynamics		Refer to Appendix 2																
Immunogenicity		Refer to Appendix 2																
Adverse Event Review	X	X		X		X			X		X		X			X		X
Concomitant Medications Review	X	X		X		X			X		X		X			X		X

^a When multiple procedures are scheduled for the same time point, PK and PD samples will be taken at the protocol assigned time point as specified in Appendix 2 and other non-PK and non-PD measurements will be taken before (ie, vital signs) or after (ie, AE review, clinical laboratory evaluation) the protocol-specified PK and PD time point. The window for PK and PD assessments is specified in Appendix 2. Unless otherwise specified, all procedures are to be completed prior to dosing with RC-P.

^b Performed at the beginning of each course with a -3 day window.

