### 10.2. Adverse Events

AEs recorded in the case report form will be coded to system organ class (SOC) and preferred term (PT) using the Medical Dictionary for Regulatory Activities (MedDRA 22.1). The investigator will assess the relatedness of each AE to study drug. The severity of AEs will be recorded using the Common Terminology Criteria for Adverse Events (CTCAE 5.0).

At a minimum, the investigator must record all AEs that occur from the time written informed consent is obtained until screen failure if applicable, or 30 days after the patient's last dose of the last course of RC-P, regardless of their relationship to study drug. Any serious AE (SAE) assessed as related to study drug by the investigator that occurs more than 30 days after the patient's last dose of the last course of RC-P should be reported regardless of time after study termination.

A treatment-emergent adverse event (TEAE) is defined as any event with onset date on or after Study Day 1 through the end of the study or any ongoing event that worsens in severity after Study Day 1 through the end of the study. Only TEAEs with the onset date through the end of the AE reporting period will be included in summary tables unless otherwise specified. For the purpose of calculating treatment emergence, incomplete onset dates will be imputed as detailed in [Appendix I](#).

AEs are graded by the investigator as Grade 1 (mild), Grade 2 (moderate), Grade 3 (severe or medically significant but not immediately life-threatening), Grade 4 (life-threatening consequences), or Grade 5 (Death related to AE). The severity grade of events for which the investigator did not record severity will be categorized as "missing" for tabular summaries and data listings, and will be considered the least severe for the purposes of sorting for data presentation.

Treatment-related AEs are those for which the investigator answers "Yes" to the question "Was this adverse event related to study treatment?" in the eCRF. Events for which the investigator did not record relationship to study treatment will be considered related to study treatment for summary purpose. Data listings will show treatment-relationship as missing. AEs for which "Yes"

Jazz Pharmaceuticals Ireland Limited  
Statistical Analysis Plan – Protocol JZP458-201

is marked for question “Was this adverse event related to study procedure?” in eCRF will be identified and included in AE listing.

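### The End of Study window opens on day 27, which conflicts with the protocol's own minimum of 30 days' follow-up and leaves up to 3 days without a scheduled adverse event enquiry

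*Protocol*

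**What the plan says.** Protocol Section 3.4 sets a floor on follow-up: "Each patient will be followed for at least 30 days following their last dose of the last course of RC-P". The synopsis (Duration of Treatment) says the same.

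Protocol Appendix 1 gives the timing of the End of Study visit in the Monday, Wednesday and Friday start schedules alike as "30 days (±3) after last dose", with the weekday row limited to Monday to Friday. That column holds the last scheduled AE review.

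Protocol Section 6.7.6.5 sets the recording period. AEs are recorded from consent "until 30 days after the patient's last dose of the last course of RC-P, regardless of their relationship to study drug". After that, only related serious events have to be reported: "any SAE assessed as related to study drug by the Investigator that occurs more than 30 days after" the last dose. SAP Section 10.2 repeats the recording period and ties the tables to it: "Only TEAEs with the onset date through the end of the AE reporting period will be included in summary tables unless otherwise specified".

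Under Protocol Section 6.7.6.6, follow-up of an unrelated AE may stop when it resolves or stabilises, or when "the event is otherwise explained, or the final study visit occurs, whichever comes first".

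**The concern.** The minus side of the ±3-day window permits something that Section 3.4 does not. A site can book a visit that is fully compliant with Appendix 1 and still fall short of the follow-up minimum in the body of the protocol. No AE review is scheduled after that visit. The later activities are reporting of related serious events, follow-up of AEs already known, and antibody samples to about 6 months in antibody-positive patients. None of these is a planned enquiry about new AEs.

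The primary safety endpoint is the occurrence of treatment-emergent AEs. For patients seen before day 30, onsets in the remaining days up to day 30 belong in the tables but reach the site only if they come to its attention in some other way. Any event missed for this reason would lower a count; none could be added.

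**Working it through.** No power or sample-size formula applies; this is calendar arithmetic. Day n below means n days after the last dose.

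**The plan's own figure.** Section 3.4 says of a patient with one course that "their study duration will be approximately 72 days". Its components are up to 28 days of screening, a 2-week course and 30 days of follow-up: 28 + 14 + 30 = 72, so the figure reproduces. It uses the full 30 days. With a visit at the earliest limit, the same sum is 28 + 14 + 27 = 69.

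**Window limits.** Lower: 30 − 3 = day 27. Upper: 30 + 3 = day 33. Days of the recording period left after a visit on day v (v ≤ 30): 30 − v. At v = 27 this is 3 of the 30 days.

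**Weekday restriction.** Protocol Table 1 gives the weekday of dose 6: Friday for a Monday start, Monday for a Wednesday start, Wednesday for a Friday start. Since 27 = 3 × 7 + 6, day 27 falls one weekday before the weekday of the last dose. Counting on from there:

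| Start of last course | Dose 6 | Day 27 | Day 30 | Permitted days (Mon–Fri) | Permitted before day 30 | Largest gap, 30 − v |
|---|---|---|---|---|---|---|
| Monday | Friday | Thursday | Sunday | 27, 28, 31, 32, 33 | 27, 28 | 3 days |
| Wednesday | Monday | Sunday | Wednesday | 28, 29, 30, 31, 32 | 28, 29 | 2 days |
| Friday | Wednesday | Tuesday | Friday | 27, 28, 29, 30, 33 | 27, 28, 29 | 3 days |

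For an on-schedule Monday start, the nominal day 30 is always a Sunday and cannot be booked. The visit must be early (day 27 or 28) or late (day 31 to 33).

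**Passages side by side.** Section 3.4 and the synopsis state a minimum duration of follow-up. Appendix 1 permits a shorter one. Section 6.7.6.5 and SAP 10.2 fix the date to which AEs are recorded, not the earliest date of a visit. They do not themselves conflict with a ±3 window. The conflict in wording is between Appendix 1 on one side and the synopsis and Section 3.4 on the other.

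**The case against.** The strongest reply is that the visit date does not close the recording period. The duty in Section 6.7.6.5 runs to day 30 whenever the visit takes place. Section 6.7.6.1 accepts AEs from any source, including reports by the patient. Related serious events remain reportable after day 30. This stands: the gap is a missing scheduled enquiry, not a period in which events go unrecorded.

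A reader might infer that no one asks these patients about the last days. The documents do not support that. They show only that no protocol AE review is scheduled then. Other chemotherapy continues under each patient's original treatment plan, so sites may see the patients anyway, although no such contact is specified.

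A reader might also infer that the SAP counts patients seen early as completely observed. It does not say so. SAP 10.2 reports numbers and percentages of patients and limits which onset dates count; it makes no statement about completeness of observation.

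It may also be tempting to see a second gap in the closing pregnancy test. Section 6.7.7 makes pregnancies arising up to 30 days after dosing reportable on first knowledge, whatever the date of that test, so the point adds little.

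Finally, some tolerance is needed, because a Monday-to-Friday visit cannot always fall on day 30. That justifies a window. It does not justify one that opens before the protocol's stated minimum.

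**Conclusion.** The point holds as a small internal conflict. Appendix 1 allows the last scheduled AE review from day 27, while the synopsis and Section 3.4 require at least 30 days of follow-up. For patients seen early, the final days have no scheduled enquiry: at most 3 days for Monday and Friday starts and at most 2 for Wednesday starts.

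These limits assume that the last dose is dose 6, given on its scheduled weekday. They also take the AE reporting period in SAP 10.2 to end at day 30 for the general run of AEs, as Section 6.7.6.5 indicates. The documents do not say how many patients would be seen before day 30, so the number of treatment-emergent AEs missed cannot be estimated; it may be none.

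Nothing else in the design depends on this visit. The primary efficacy endpoint is measured in Course 1, and the Study Data Review Committee reviews of Part A and the interim and primary analyses are triggered by completion of Course 1. Safety has no formal testing. This is a worthwhile tidy-up, not a threat to the trial's conclusions.

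**What to change.** Reconcile Appendix 1 with the synopsis and Section 3.4 in one of two ways.

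- **Plus-only window.** Set the End of Study visit at, for example, 30 +3 days in all three schedules. Weekdays remain for every on-schedule start: days 31, 32 and 33 (Monday start), days 30, 31 and 32 (Wednesday start), and days 30 and 33 (Friday start).
- **Keep ±3 for sampling and add an AE contact.** Require one documented AE contact on or after day 30 for anyone whose visit took place before then.

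The first option is an edit to three tables. It costs some booking flexibility, with only two usable weekdays for an on-schedule Friday start. The second keeps the flexibility at the price of one brief contact per patient seen early. Either makes safety ascertainment slightly more complete and lets a visit that complies with the schedule also comply with Section 3.4.

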APPENDIX 3. SUMMARY OF CHANGES**Amendment 02**

Amendment 02 was initiated to allow additional higher dose subcohorts to be investigated if warranted by the data. Following is a list of the important changes in Amendment 02. Editorial changes and changes that do not impact patient care or safety are not included in this list. The following changes were also applied to the text in the synopsis.

Section Number of First Occurrence	Description of Change	Brief Rationale
Section 1.4	Allow testing of additional subcohorts at higher doses above 37.5 mg/m ² with each additional dose level(s) not to exceed a 50% increase from the previous dose level.	The dose cap of 80 mg/m ² was removed because the available preliminary PK modeling data has shown that higher doses than 80 mg/m ² may be necessary to achieve the objectives of the current protocol. The current plan to not exceed a 50% increase from the previous dose level with each additional dose level and the safety monitoring outlined in the protocol are appropriate to ensure patient safety in the study.
Sections 6.7.3.2 and 6.7.5	Standardized the testing window from 3 to 7 days for all laboratory tests, including coagulation tests and laboratory tests at Screening.	To clarify the timing of the testing window for laboratory tests at study sites.

Amendment 01

Amendment 01 was initiated to allow additional dose subcohorts to be investigated if warranted by the data, and to allow Part B to be conducted in parallel with Part A. Following is a list of the important changes in Amendment 01. Editorial changes and changes that do not impact patient care or safety are not included in this list. The following changes were also applied to the text in the synopsis.

Section Number of First Occurrence	Description of Change	Brief Rationale
Section 1.4	Allow testing of additional subcohorts at higher doses above 37.5 mg/m ² with each additional dose level(s) not to exceed a 50% increase from the previous dose	The cap of 80 mg/m ² is based on the available preliminary PK modeling data.

RC-P
Protocol Amendment 02: JZP458-201

Jazz Pharmaceuticals Ireland Limited

Section Number of First Occurrence	Description of Change	Brief Rationale
	level and no dose level to exceed 80 mg/m ² .	
Section 3.1	Allow enrollment into Part B (IV formulation) to begin before completion of Part A (IM formulation); study center participation will be at the discretion of the Sponsor.	The IV route of administration is important, particularly in the pediatric setting, and allowing separate study centers to enroll in Part B while Part A is being completed will expedite a potential treatment option to address an unmet medical need.
Section 3.1.3.1	Based on all of the data, the SDRC may recommend that a different dose be given on Fridays than on Mondays and Wednesdays.	A new dose may need to be explored to ensure adequate dosage coverage for up to 72 hours.
Section 4	Removed the limit on the number of study centers and expand study globally.	Additional study centers outside of North America will be included in the study to increase the availability of the investigational product to patients.
Section 4.1, Inclusion Criterion #5	Specified that the undetectable SAA levels should be based on the lower limit of quantification, as defined by a certified laboratory authorized under CLIA to perform this testing.	CLIA-certified laboratories utilize different limits of quantification depending on their assay methodologies, and results to determine undetectable SAA levels may vary between laboratories.
Section 6.6	Indicated that serum asparaginase concentration is the same as PK Content for this study.	Created alignment between the SAP (which uses serum asparaginase concentration) and the label on the laboratory tubes (which uses PK Content).
Section 6.7.1	Removed time window for collection of vital signs.	The assessment of vital signs within 15 minutes of the pre-dose sample collections is not consistent with typical clinical practice, particularly in the setting of a busy pediatric hematology oncology clinic.
Section 6.7.1	Removed respiratory rate as a required assessment; respiratory rate may be collected if it is a standard of care at the study center.	The collection of respiratory rate is not a standard assessment preferred in the patient population.
Section 6.7.3.2	Updated coagulation collection language to match SOE tables.	Corrected a discrepancy in the original protocol.
Section 6.7.8	Added list of AEs that would be considered anticipated.	This list was added as a request from FDA to provide clarity for expedited safety reporting.

RC-P
Protocol Amendment 02: JZP458-201

Jazz Pharmaceuticals Ireland Limited

## 1. LIST OF ABBREVIATIONS

**Table 1: List of Abbreviations**

Abbreviation	Term
ADA	Anti-drug antibody
AE	Adverse event
ALL	Acute lymphoblastic leukemia
BSA	Body surface area
CI	Confidence interval
COG	Children's Oncology Group
CSR	Clinical study report
CTCAE	Common terminology criteria for adverse events
CV	Coefficient of variation
E. coli	Escherichia coli
eCRF	Electronic case report form
EDC	Electronic data capture
FDA	Food and Drug Administration
ICH	International Council for Harmonisation
IM	Intramuscular
IU	International unit(s)
LBL	Lymphoblastic lymphoma
IV	Intravenous
MedDRA	Medical Dictionary for Regulatory Activities
NSAA	Nadir serum asparaginase activity
PD	Pharmacodynamics
PK	Pharmacokinetic
PT	Preferred term
RC-P	Recombinant crisanaspase produced in Pseudomonas fluorescens
SAA	Serum asparaginase activity
SAE	Serious adverse event
SAP	Statistical analysis plan
SD	Standard deviation
SDRC	Study data review committee
SOC	System organ class

Jazz Pharmaceuticals Ireland Limited  
Statistical Analysis Plan – Protocol JZP458-201

SOP	Standard operating procedures
TEAE	Treatment emergent adverse event
WHO	World Health Organization

Jazz Pharmaceuticals Ireland Limited  
 Statistical Analysis Plan – Protocol JZP458-201

## 2. MODIFICATION HISTORY

Version History for SAP:

Version	Date	Description
1.0	18DEC2019	Original
1.1	07APR2020	Clarification on the Efficacy/PK/PD Analysis Sets and sample size at the interim analysis in Section 5.3
1.2	08JUN2020	Further clarification and language update on the sample size at the interim analysis in Section 5.3
1.3	24SEP2020	
 
• Update study design in Section 5 per protocol amendment 1 and 2.
 
• Clarification on the sample size at the primary analysis in Section 5.3.
 
• Addition of the sensitivity analyses to assess COVID-19 impact on the primary (Section 9.1.3) and key secondary (Section 9.2.3) efficacy endpoints.
 
• Addition of Section 13. COVID-19
 

1.4	16DEC2020	
 
• Added the term of pulmonary embolism to the list of preferred terms for the AE of special interest of thrombosis.
 

Jazz Pharmaceuticals Ireland Limited  
Statistical Analysis Plan – Protocol JZP458-201

